5.1.2 Patient Positioning

All patients will undergo CT simulation in positioning appropriate for the specific treatment site for proton therapy. When medically feasible and applicable, patients may be simulated with IV and/or small bowel contrast (for non-thorax cases).

5.1.3 Treatment Volume Definition: Gross Tumor Volume (GTV), Clinical Target Volume (CTV), and Planning Target Volume (PTV)

Gross Tumor Volume (GTV) should include all gross recurrent disease including lymph node metastases as determined by CT, PET/CT, MRI, or biopsy.

The treatment target volumes and creation of the CTV and PTV are disease site specific and will be at the discretion of the treating radiation oncologist. Initial treatment pre-plan based on CT simulation will thus be generated with above target information. Additional treatment volumes including PTV_Opt and ring optimization structures may be generated for the purpose of adaptive treatment plan optimization. The decision to use PTV_Opt will be dependent on site of disease and anatomical location. This will be decided during initial treatment planning with treating radiation oncologist and physicist after simulation but prior to treatment start.

5.1.4 Organs at Risk Contours and Dose Constraints

OAR/normal structure contours and dose constraints will be disease site specific and to the discretion of the treating radiation oncologist. Generally, dose constraints will adhere to standard of care institutional dose constraints employed here at WashU/BJC Radiation Oncology Department.

5.1.5 Initial Treatment Planning

Coverage goal will be for 95% of the target volume or optimization volume to be covered by 95% of the dose. In situations where a critical structure is violated, reduction of dose or volume will be allowed in areas of overlap.

5.1.6 Adaptive Treatment Planning

When patients present for each proton treatment session, the initial treatment pre-plan will be generated based on the anatomy of the day. In addition to this, a new adapted treatment plan will be generated and re-optimization will be performed for dose adaptation to allow for acceptable sparing of normal structures (i.e., not violating the predetermined hard constraints based on safety constraints that are

already approved of for routine, clinical use). Dose adaptation can also be done in cases where on the volumetric imaging attained, there is noted to be violation of previously met hard constraints.

The supervising physician will review the adapted plan and prior non-adapted scheduled plan. Comparison will be made with initial pre-plan assessing for meeting OAR constraints and/or improvement of target coverage. The decision to proceed with the adaptive radiation is under the treating physician's clinical discretion where they feel tumor coverage may be impacted by interfraction motion of patient's anatomy and adaptive treatment may improve coverage based on pre-specified criteria (typically improvement in radiation dose coverage of the tumor or reduction of excess dose to a nearby organ which would increase toxicity). Subsequently, decision will be made if treatment will proceed with adapted plan or with initial pre-plan.

5.1.7 Quality Assurance of the Adaptive Plan

Patient specific QA will be performed at each fraction prior to delivery of the adaptive treatment plan. Given that dose measurements will not be possible with the patient on the table, this will be achieved by performing an independent Monte Carlo dose calculation on the image of the day, using the exported beam parameters, and mapped electron density. The independently calculated dose distribution will be compared to the dose distribution exported from Raystation, proton therapy planning system, looking at dose volume histograms and 3D gamma analysis of all voxels within the patient. An in-house plan integrity verification algorithm will be utilized to evaluate plan quality and integrity via plan parameters including contours, beam angles, segments, and monitor units. After completion of the automated checks, a final review by physics will be required prior to proceeding to treatment delivery. Following the completion of each treatment fraction, there will be an additional QA process conducted offline to verify the integrity of the delivered treatment and ensure that the dose administered aligns with the expected dose.

5.1.8 Dose Constraints

As this is a feasibility study, patients participating in the trial will have various types of malignancies in different anatomical locations, clinical circumstances, and different prescribed doses and treatment schedules. The dose constraints for each patient will be specific to their individual anatomy and will be determined during the initial treatment planning process by the treating radiation oncologist. Specific dose constraints will be established on a case-by-case basis. Generally, dose constraints will adhere to standard of care institutional dose constraints employed here at WashU/BJC Radiation Oncology Department. Below is suggested dose constraints for 5 fraction SBRT. The dose constraints listed below may be modified based on individual patient's clinical scenario and discretion.

Structure	Goal	Variation
Brachial Plexus	D0.1cc < 30.5Gy	D 0.1cc < 32Gy
Chest Wall	D0.1cc < 43Gy	
Spinal Cord	D0.5cc < 25Gy	
Lungs	V20Gy < 10%	V20Gy < 15%
Esophagus	D0.5cc < 33Gy	D0.5cc < 36Gy
Heart	D0.1cc < 29Gy	D0.1cc < 38Gy
Liver - GTV	Critical Volume >700cc < 15Gy V10Gy < 70%	
Kidney	Bilateral mean <15 Gy	
Stomach	D0.5cc < 33Gy	D0.5cc < 36Gy
Duodenum	D0.5cc < 33Gy	D0.5cc < 36Gy
Small Bowel	D0.5cc < 33Gy	D0.5cc < 36Gy
Large Bowel	D0.5cc < 33Gy	D0.5cc < 36Gy
Rectum	D0.1cc < 38Gy	
Bladder	D0.1cc < 38Gy	

5.2 Definitions of Evaluability

Endpoint	In order to be evaluable for this endpoint, a patient must...
Primary: feasibility of online proton adaptive radiotherapy	Have received at least one fraction of SBRT.
Secondary: G2+ toxicity at 3 months	
Exploratory: dosimetry evaluation and comparison to non-adaptive workflow	
Exploratory: PREMs	Have received at least one fraction of SBRT and completed PREMs.

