1.7 Risk/Benefit Assessment

1.7.1 Known Potential Risks

The medical risks from participating in this study revolve around exposure to proton radiation and increased time required per treatment to allow for day of plan adaptation. Treatment options for patients enrolled in this study include irradiating with online adaptive stereotactic body radiation treatments (SBRT) over 5 days every day or every other day to a dose of 25-50 Gy. All patients undergoing five fractions or fewer fractions with protons would be evaluated for eligibility for this study during a twice weekly proton triage meeting. Patients enrolled in this study would be deemed appropriate for non-adaptive proton SBRT by the treating radiation oncologist.

Adaptive radiation planning enables improved target coverage by accounting for daily changes in anatomy. This results in a higher integrated dose to the tumor, which has the potential of increased radiation toxicity. However, similar studies of photon based radiation adapted planning have shown this approach to be safe, with comparable levels of acute toxicity seen in both adapted and non-adapted conventional plans.

With online adaptation radiation treatment plans, the time a patient spends lying on treatment table may be extended (45-90 minutes) compared to non-adapted conventional plans (20-30 minutes).

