2.0 OBJECTIVES AND ENDPOINTS

Objectives	Endpoints
Primary	
To assess the feasibility of online proton adaptive radiotherapy based on successful delivery of more than 70% of attempted fractions where treatment adaptation is indicated.	
Successful completion of online adaptive proton radiotherapy workflow through treatment delivery in at least 70% of planned adaptive fractions.
 
Success will be defined as PARTy plan creation and delivery of the fraction using the study workflow in one on-table attempt. Unsuccessful planning and workflow delivery will be defined as multiple attempts of the PARTy workflow for one treatment fraction without treatment delivery such that the study workflow is abandoned.

Secondary	
1. To assess the safety of online proton adaptive radiotherapy.	1. Grade 2+ radiation-related toxicity at 3 months as measured by CTCAE v5.0.
Exploratory	

 To assess patient tolerability and satisfaction with online proton adaptive radiotherapy process. To assess dosimetric differences for target coverage and organ at risk (OAR) sparing between adaptive and non-adaptive proton therapy. 	
 Patient reported experience measures (PREMs). Dosimetry evaluation and comparison to non-adapted pre-plan.

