4.4 OnCore Subject Status Definitions

Note: subject status should not be updated in OnCore until the subject is actively in that status; future dates are not allowed.

Subject Status	Definition
Consented	Patient has signed an IRB approved consent for the trial.
Eligible	Patient eligibility has been confirmed by Washington University PI or delegate.
Not Eligible	Patient did not meet eligibility criteria for the trial. Note that if a patient is determined to be eligible but never initiates study participation, they are not considered a screen fail.
On Study	Patient is confirmed eligible for the study and enrolled.
On Treatment	Patient is receiving study therapy. On Treatment date should be the date of the first study treatment.

Off Treatment	Patient has discontinued study therapy. Off Treatment date should be the last day any study treatment was administered.
On Follow Up	On Follow Up date is the same as the Off Treatment date
Off Study	Patient has fully discontinued all study procedures (including any follow-up procedures and/or review of medical record for outcomes data).

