11.0 STATISTICAL CONSIDERATIONS

11.1 Definition of Primary Endpoint

Feasibility: Feasibility will be defined as successful completion of online adaptive proton radiotherapy workflow through treatment delivery in at least 70% of planned adaptive fractions..

Success will be defined as PARTy plan creation and delivery of the fraction using the study workflow in one on-table attempt. Unsuccessful planning and workflow delivery will be defined as multiple attempts of the PARTy workflow for one treatment fraction without treatment delivery such that the study workflow is abandoned.

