11.3 Sample Size Calculation

As a pilot study, the sample size is determined based on clinical considerations rather than statistical power. For our primary objective, our goal will be to report the description of online adaptive proton therapy treatment workflows, adaptation, and the time to delivery of first treatment fraction. Goal accrual will be 10 evaluable patients. For the exploratory objectives, sample size is also based on clinical considerations rather than statistical power.

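### Evaluability for the primary feasibility endpoint requires a delivered SBRT fraction, so a patient whose adaptive workflow is abandoned and who leaves untreated drops out of the success rate

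*Combined protocol and SAP*

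**What the plan says.** The evaluability table in section 5.2 gives the condition for the primary feasibility endpoint as "Have received at least one fraction of SBRT". It asks for SBRT, not adaptive SBRT.

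Section 11.3 states: "Goal accrual will be 10 evaluable patients". It adds that "the sample size is determined based on clinical considerations rather than statistical power". No section says whether a non-evaluable patient is replaced.

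Section 11.1 defines success as creating the adapted plan and delivering the fraction with it in one on-table attempt. It defines failure as "multiple attempts of the PARTy workflow for one treatment fraction without treatment delivery such that the study workflow is abandoned".

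The denominator is worded in two ways. Section 11.1 requires completion "through treatment delivery in at least 70% of planned adaptive fractions". The objective in section 2.0 refers to "successful delivery of more than 70% of attempted fractions where treatment adaptation is indicated", and section 11.4 likewise refers to fractions where adaptation is indicated.

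Sections 5.0 and 5.1.6 have both the pre-plan and an adapted plan prepared at each session, and treatment may go ahead on either. Section 1.7.1 says that enrolled patients are suitable for non-adaptive proton SBRT. Section 5.5 keeps patients who stop early in follow-up, but does not say how they enter the primary rate.

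**The concern.** The endpoint asks whether a fraction can be planned and delivered with the workflow. Entry to the analysis set requires that some fraction was delivered, so membership depends partly on the outcome being measured.

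The patient at issue is narrowly defined: the adaptive workflow is started and abandoned, and the patient then leaves before any SBRT fraction is given. The route is plausible. Section 1.7.1 expects 45 to 90 minutes on the table, against 20 to 30 without adaptation, and section 5.5 allows withdrawal at any time. This patient's attempt bears directly on feasibility, yet it is not counted.

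Section 11.4 uses the 70% figure to decide whether the pilot supports wider study, and relies on descriptive statistics. An exclusion that can only remove failures pushes that decision one way.

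**Working it through.** **The plan's own figure.** The only sample-size figure is 10 evaluable patients, set on clinical grounds, so there is no power calculation to reproduce. With five fractions each (section 5.1.1), the maximum is 10 × 5 = 50 fractions.

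**Inputs.**
- N = 50 fractions from evaluable patients. This assumes that all are adaptation-indicated, which the documents do not say.
- S = successful fractions among those 50.
- k = patients who leave after an abandoned attempt with no SBRT fraction delivered. The documents give no frequency, so k = 0, 1 and 2 are shown.
- Each such patient adds one attempted, failed fraction and no success.

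**Formula.** The rate under section 5.2 is S/N. The rate with these patients counted is S/(N + k). The second can never exceed the first, so the direction is fixed. The fall is (S/N) × k/(N + k). For S = 36 and k = 1 it is 0.72 × 1/51 = 0.014, or 1.4 percentage points.

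| S | Section 5.2 rate | k = 1 | k = 2 |
|---|---|---|---|
| 35 | 35/50 = 70.0% | 35/51 = 68.6% | 35/52 = 67.3% |
| 36 | 36/50 = 72.0% | 36/51 = 70.6% | 36/52 = 69.2% |
| 40 | 40/50 = 80.0% | 40/51 = 78.4% | 40/52 = 76.9% |

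**How many such patients a result can absorb.** The rate stays at or above 70% while k ≤ S/0.70 − 50.
- S = 36: 51.4 − 50 = 1.4, so one patient.
- S = 40: 57.1 − 50 = 7.1, so seven.
- S = 45: 64.3 − 50 = 14.3, so fourteen.

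**Successes needed among the 50 evaluable fractions.** Under at least 70%, the number is 35 with k = 0, 36 with k = 1 and 37 with k = 2. Under more than 70%, it is 36, 36 and 37. On the stricter wording a single such patient does not move the bar.

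**Chance of passing, under at least 70%.** Fractions are treated as independent binomial trials. This ignores clustering within patients, so the figures are illustrative. At a true success rate of 0.70 among evaluable patients, P(at least 35 of 50) = 0.569 under section 5.2, against P(at least 36 of 50) = 0.447 once one such patient is counted. At a true rate of 0.80 the figures are 0.969 and 0.939.

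**Fewer indicated fractions.** If only 20 fractions were indicated, each case weighs more: 14/20 = 70.0% becomes 14/21 = 66.7%, and 15/20 = 75.0% becomes 15/21 = 71.4% with one patient and 15/22 = 68.2% with two.

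**The case against.** **Most first-attempt failures stay in.** A reader might infer that any patient whose first adaptive attempt fails is dropped. The documents do not support that. Section 5.2 says SBRT, and sections 5.0 and 5.1.6 allow the fraction to be given on the pre-plan. One pre-plan fraction, or any later fraction, keeps the patient evaluable and the failure countable. Only patients with no delivered fraction at all are lost. This objection stands and limits the point.

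**Replacement is not a stated rule.** It follows only by implication from accruing to 10 evaluable patients. This also stands, but the exclusion matters even without replacement.

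**Larger effects need another denominator.** If all five planned fractions of each departed patient counted, 36/50 would become 36/55 = 65.5% with one and 36/60 = 60.0% with two. Those figures include four fractions per patient that were never attempted. They depend on the unresolved difference between planned fractions in section 11.1 and attempted, indicated fractions in section 2.0. They are not relied on here.

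**A pre-plan-only patient is not a source of bias.** Someone with no adaptation-indicated fraction can fill one of the 10 places. On the section 2.0 denominator that patient adds nothing to numerator or denominator, so information is lost but the rate is not distorted.

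**A single abandoned attempt is not clearly a failure.** Section 11.1 requires multiple attempts, so one abandoned attempt fits neither definition. This is correct, and the fix must cover it.

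**Monitoring gives some visibility.** The reports in section 9.0 list patients started, discontinued and evaluable per objective, and Appendix D records reasons for discontinuation. That would show such losses to the monitoring committee but would not put the failures back into the rate.

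**This is a small descriptive pilot.** True, but its 70% rule still drives a stated decision.

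**Conclusion.** The point holds in a limited form. Section 5.2 makes entry to the primary analysis depend partly on delivery, which is itself part of the endpoint. A patient who leaves after an abandoned adaptive attempt with no SBRT fraction delivered is excluded and may, by implication, be replaced. Any bias runs toward declaring feasibility.

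The size is modest on attempted fractions: about 1.4 percentage points per such patient near the threshold when 50 fractions are indicated, and more when fewer are. Two such patients turn 72.0% into 69.2%, which fails under either wording of the threshold. One leaves 70.6%, which passes under either. A result of 80.0% is not reversed by two. If no such patient occurs, the bias is zero.

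These figures rest on two assumptions that are not in the documents: the number of indicated fractions, and how often a patient leaves untreated after an attempt. A reader should not conclude that the trial will be biased, or that early failures are routinely discarded. What the documents show is a rule that would leave out this kind of failure if it occurred.

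**What to change.** In section 5.2, define the primary analysis set as every enrolled patient with at least one fraction for which adaptation was indicated and the on-table PARTy workflow was attempted, whether or not any SBRT fraction was delivered. On-table CT acquisition alone should not be the trigger: it happens at every session, so patients always treated on the pre-plan would qualify too.

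Count each such fraction that does not end in delivery of the adapted fraction as a failure, whether or not pre-plan treatment follows. Align the failure definition in section 11.1 so that a single abandoned attempt is also classified. Because section 5.1.6 places the choice between plans after the adapted plan exists, say how indication is recorded when an attempt stops before that comparison.

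In section 11.3, state that patients in this set are not replaced, that only patients with no attempted adaptive fraction may be replaced, and that the number of replaced patients and the reasons are reported.

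The cost is wording only, with no added study procedures. The reported rate may be slightly less favourable. Settle the text before results are known, since near 70% a later decision on whether an early failure counts could determine the conclusion.

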Description of Study Intervention:	Patients planning to receive standard of care proton therapy will be consented to the study. After study enrollment, at time of each daily or every other day fraction, patients will undergo online evaluation for proton replanning based on prespecified dosimetric objectives of improving tumor coverage and/or normal organ at risk sparing.
Study Duration:	12 months accrual + 3.5 months for patient treatment and follow-up + 3 months analysis = 18.5 months
Participant Duration:	1 to 2 weeks of treatment + 3 months follow-up = 3.5 months

SCHEMA

SCHEDULE OF ACTIVITIES

Screening assessments should occur within 4 weeks prior to the start of SBRT unless otherwise noted. The window for the 3 mos post-Tx visit is +/-4 weeks.

Daily SBRT Schedule							
	Screening	D1	D2	D3	D4	D5	3 mos post-Tx
Informed consent	X						
Medical history	X						
H&P	X						X
Volumetric imaging ¹	X						
Pregnancy test ²	X						
Diagnostic scan based preplan ³	X						
Adaptive proton SBRT		X	X	X	X	X	
Patient Reported Experience Measures						X ⁴	
Adverse events assessment		X-----X					

¹ CT, MRI, or PET are acceptable as per routine clinical evaluation at the discretion of the treating physician.

² Women of childbearing potential only; within 14 days prior to the start of treatment.

³ Initial radiation treatment plan based on standard CT simulation.

⁴ Questionnaire of patients' experience with adaptive workflow, given at the end of the last treatment (window +7 days).

Every Other Day SBRT Schedule ⁵							
	Screening	D1	D3	D5	D7	D9	3 mos post-Tx
Informed consent	X						
Medical history	X						
H&P	X						X
Volumetric imaging ¹	X						
Pregnancy test ²	X						
Diagnostic scan based preplan ³	X						
Adaptive proton SBRT		X	X	X	X	X	
Patient Reported Experience Measures						X ⁴	
Adverse events assessment		X-----X					

¹ CT, MRI, or PET are acceptable as per routine clinical evaluation at the discretion of the treating physician.

² Women of childbearing potential only; within 14 days prior to the start of treatment.

³ Initial radiation treatment plan based on standard CT simulation.

⁴ Questionnaire of patients' experience with adaptive workflow, given at the end of the last treatment.

⁵ RT will not be administered on a weekend; a 2 day break in between fractions due to scheduling is acceptable (window +7 days).

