5.5 Duration of Therapy

If at any time the constraints of this protocol are considered to be detrimental to the patient's health and/or the patient no longer wishes to continue protocol therapy, the protocol therapy should be discontinued and the reason(s) for discontinuation documented in the case report forms.

In the absence of treatment delays due to adverse events, treatment may continue for a total of 5 fractions of SBRT or until one of the following criteria applies:

- Documented and confirmed disease progression
- Intercurrent illness that prevents further administration of treatment
- Death
- Unacceptable adverse event(s)
- General or specific changes in the patient's condition render the patient unacceptable for further treatment in the judgment of the investigator
- Suspected pregnancy
- Serious non-compliance with the study protocol
- Lost to follow-up
- Patient decides to withdraw from the study
- The Siteman Cancer Center decides to close the study

Patients who prematurely discontinue treatment for any reason will still be followed as indicated in the study calendar.

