11.2 Definition of Secondary and Exploratory Endpoints

Secondary

Toxicity: This will be evaluated throughout treatment and at 3 months post-end of SBRT using CTCAE v5.0. Grade 2+ radiation-related toxicity will be collected.

Patient satisfaction: This will be evaluated using patient reported experience measures (PREMs, Appendix E) at the end of treatment.

Dosimetry evaluation: PARTy dosimetric evaluation will be completed with a goal of comparing the dose to OARs and target coverage in online adapted treatment plan with the non-adapted treatment plan.

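### Section 5.2 limits the tolerability and satisfaction analysis to patients who completed the PREM, so early stoppers may be left out and the result is at risk of bias towards satisfaction

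*Combined protocol and SAP*

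**What the plan says.** Section 2.0 states the exploratory objective as "To assess patient tolerability and satisfaction with online proton adaptive radiotherapy process", with the PREM as its endpoint.

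Section 5.2 sets evaluability. For the primary endpoint a patient must "Have received at least one fraction of SBRT". The toxicity and dosimetry rows are blank in the extracted table and appear to share that cell. The PREM row alone adds a second condition: "Have received at least one fraction of SBRT and completed PREMs".

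On timing, both schedules mark the form once, in the D5 or D9 column, and the footnotes say it is "given at the end of the last treatment". Section 8.0 makes it due when treatment is completed. Section 11.2 says of satisfaction: "This will be evaluated using patient reported experience measures (PREMs, Appendix E) at the end of treatment".

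On early stopping, section 5.5 lists among its reasons "Patient decides to withdraw from the study" and unacceptable adverse events, and requires the reason to be recorded in the case report forms. It then adds: "Patients who prematurely discontinue treatment for any reason will still be followed as indicated in the study calendar".

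Section 11.4 plans descriptive statistics for the PREM. It gives no rule for missing forms, no denominator of all treated patients and no tabulation of those without a form.

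**The concern.** The objective asks how the adaptive process is borne by the patients put through it. The analysis set is defined by having the outcome, so the question answered is how satisfied the patients were who returned a form.

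The difference matters if forms go missing for reasons linked to the experience itself. The protocol names a plausible link: section 1.7.1 expects 45-90 minutes on the table, against 20-30 minutes for non-adapted plans. A patient who leaves because of that burden is central to this objective and is plausibly less likely to return a form at the end of treatment. Removing that patient from the denominator would make the process look better accepted than it was. Section 11.4 presents the pilot's descriptive results as baseline values, so an optimistic figure could carry into later work.

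**Working it through.** The plan gives no expected completion rate, dropout rate or target for the PREM, so there is no figure to reproduce. The check has two parts.

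**1. Who enters the analysis under the current text**

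| Patient | Section 5.2, PREM row | Form offered? |
|---|---|---|
| Five fractions, form returned | Evaluable | Yes |
| Five fractions, form not returned | Not evaluable | Yes |
| Stops early, form returned | Evaluable | Not stated outright; possible if the last treatment means the last one received |
| Stops early, no form | Not evaluable | Not stated outright |

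The exclusion therefore works through the missing form, not through early stopping as such.

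**2. How far missing forms could move a result**

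Inputs:
- N = 10 treated patients. Section 11.3 sets the goal at 10 evaluable patients; I take evaluable in the primary-endpoint sense of at least one fraction.
- k = number of treated patients without a form, from 0 to 3 (assumption).
- s = number of completers counted as satisfied (assumption; the plan defines no such cut on the 1-4 items of Appendix E).

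Formulas: completers-only = s/(N − k); all-treated worst case = s/N; all-treated best case = (s + k)/N. The gap between best and worst is k/N, which is 10 points per missing form when N = 10.

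If every completer is satisfied (s = 10 − k):

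| k | Completers-only | All-treated, worst to best |
|---|---|---|
| 0 | 10/10 = 100% | 100% to 100% |
| 1 | 9/9 = 100% | 9/10 = 90% to 100% |
| 2 | 8/8 = 100% | 8/10 = 80% to 100% |
| 3 | 7/7 = 100% | 7/10 = 70% to 100% |

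If one completer is not satisfied (s = 9 − k):

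| k | Completers-only | All-treated, worst to best |
|---|---|---|
| 1 | 8/9 = 88.9% | 80% to 90% |
| 2 | 7/8 = 87.5% | 70% to 90% |
| 3 | 6/7 = 85.7% | 60% to 90% |

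For a mean item score, assume completers average 3.5. The all-treated mean is [3.5(10 − k) + v·k]/10, with v = 1 at worst and v = 4 at best:
- k = 1: (31.5 + 1)/10 = 3.25 to (31.5 + 4)/10 = 3.55
- k = 2: (28 + 2)/10 = 3.00 to (28 + 8)/10 = 3.60
- k = 3: (24.5 + 3)/10 = 2.75 to (24.5 + 12)/10 = 3.65

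The chance of at least one missing form among 10 patients is 1 − (1 − p)^10. For assumed p of 5%, 10% and 20% it is 40%, 65% and 89%.

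**The case against.** A reader might infer that patients who stop early are shut out by rule. The documents do not support that. Section 5.2 asks for one fraction and a form, not five fractions. The last treatment can be read as the last one received, and section 4.4 dates the end of treatment to the last day any study treatment was given. Section 5.5 keeps early stoppers in calendar follow-up. This stands. What it leaves open is that no sentence says the form is given at discontinuation, both schedules mark only the fifth-fraction column, and a patient who is offered the form but does not return it still leaves the denominator.

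A reader might also infer that the result is biased. That would need forms to be missing, and missing because of intolerance. Section 5.5 also lists unrelated reasons for stopping, such as progression, intercurrent illness and closure of the study, and every range above includes the completers-only value or a higher one. This too stands: the plan carries a risk of bias, not a demonstrated bias. For the same reason, expressing the gap as a percentage overstatement would put a precise size on a statistic the plan does not define.

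It can fairly be said that intolerance is recorded elsewhere. Reasons for discontinuation go into the case report forms and, per patient, into the Appendix D tables, and treatment-related adverse events of grade 2 and above are collected. But section 7.0 keeps grade 1 events off the toxicity form, so milder discomfort on the table may not appear there. Section 11.4 does not place the reasons for stopping beside the PREM, and the four Appendix E items ask about satisfaction, with none on tolerability directly.

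Finally, counting a stop as a failure on the satisfaction form would create a new composite endpoint. That objection is sound; the change below reports such stops next to the PREM instead.

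**Conclusion.** The point holds as a minor one. The plan states a completers-only set for an objective about tolerability, schedules the form once, and does not say how missing forms are handled. Patients who could not tolerate the process may therefore be left out, and the summary is at risk of leaning towards satisfaction.

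The possible size is up to 10 percentage points of an all-treated proportion per missing form. This rests on 10 treated patients, an assumed number of missing forms and an assumed satisfied/not satisfied split. If all forms are returned, the problem disappears.

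The consequence is contained. Section 2.0 classes the endpoint as exploratory, although section 11.2 lists it under a secondary heading. The decision in section 11.4 rests on the share of fractions delivered and on safety, and neither of those endpoints carries the form-completion condition.

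**What to change.** - **Section 5.2:** make every patient who received at least one fraction evaluable for this objective, as for the other endpoints.
- **Both schedule footnotes and section 8.0:** state that the form is offered at the last fraction received or at discontinuation, within the existing +7 day window. In the daily schedule that window is attached to the form. In the every-other-day schedule it sits in the footnote on weekend breaks, so the two should be aligned.
- **Section 11.4:** report each PREM item over all treated patients, with 'form not completed' as its own category by reason. Next to it, give the number who stopped because of the procedure, using the reasons already recorded under section 5.5 and Appendix D. Show completers-only summaries second, with best- and worst-case bounds if any forms are missing.

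The cost is a few sentences. The form stays the same, and no extra patients or new data source are needed. The downside is that the figures may look slightly less favourable. The form-timing change should be made before patients stop treatment, because a form not offered then may not be recoverable. A patient who withdraws from the study may still give no form; the change makes that patient visible in the table rather than absent from it.
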